2. *Describe the methods that will be used to identify potential research participants.*

The proposed study will involve participation of male and female children to achieve a total number of 30 complete data sets. All children to be studied will range in age between 9-17 years during the funding period. Study participants will include survivors of preterm birth, with birth gestations of 22-30 weeks and birth weights appropriate for gestational age.

We intend to focus our recruitment on 20 children who were born preterm with birth gestational ages between 22-30 weeks, are survivors from Rainbow Babies & Children's Neonatal Intensive Care Unit, and have been followed since birth. The children invited for participation will be part of the maintained cohort for whom continuous oxygen saturation data were collected in their first 8 weeks of postnatal life. Co-Investigator [name] maintains this research cohort. In the event that we cannot enroll 20 children who have continuous oxygen saturation data from their neonatal hospital stay, [name] will assist us to identify other preterm survivors who are similar to the study group population but may be between 9 and 17 years old and/or have birth gestations up to 30 weeks. We will also recruit for other preterm survivors via study flyers and advertisements.

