4. Describe when research procedures will take place and the duration of an individual subject's participation in the study. Use of the descriptive table listing the study procedures that indicates the visit/week of the interventions below is encouraged.

	Pre-Screening	Visit 1	Visit 2	Visit 3	Six week Follow up
Estimated time requirement					
Data Collection	X				
Study Procedure 1		X	X	X	
Study Procedure 2		X		X	
Study Procedure 3		X		X	
Phone Call Questionnaire					x

DESIGN & DESCRIPTION: The investigators will conduct an observational study comparing two groups of children to determine whether differences in birth events and oxygen levels during the newborn period lead to structural and functional impairment within the brain's dopaminergic pathways and the cortical regions innervated by those pathways. The dopaminergic system is involved in modulating motor control and cognitive function.

Our goal is to characterize **structure** and **function** of dopaminergic pathways and the cortical regions innervated by those pathways in post-hypoxic former preterm children. We will accomplish this through the use of neuroimaging analysis techniques, such as

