- Health plan beneficiary number
- Account number
- Certificate/license number
- Any vehicle or other device serial
- Device identifiers or serial numbers
- Web URL
- Internet protocol (IP) address
- Finger or voice prints
- Photographic images
- Other: Any characteristic that would uniquely identify the individual

2. *List all other data to be collected for the research study (e.g. laboratory values, physician notes, length of stay, etc.).*

- Magnetic Resonance Imaging, specifically T1 structural scan, Diffusion Tensor Imaging (DTI), and functional Magnetic Resonance Imaging-Blood Oxygen Level Dependent (fMRI-BOLD)
- High density electroencephalography (HD-EEG)

- Neurobehavioral Assessments of child: Verbal n-back; Grooved Pegboard task
Parent report of child behavior (parent-report): Child Behavior Checklist, Vanderbilt Assessment Test, Child’s Sleep Habits Questionnaire (for children ages 9-12), Pediatric Sleep Questionnaire (for children ages 9-17).
- Urine collection (to determine pregnancy exclusion for female child participants)

Data Analysis Plan

1. Describe the data analysis plan, including any statistical procedures. Provide a power analysis if applicable.
2. If applicable, describe the primary and secondary study endpoints including safety endpoints.

Our intent in this exploratory cross-sectional two-arm pilot study is to develop sufficient Scientific Rigor to support a future study appropriately powered to account for our proposed primary outcome measures and co-variates. Our sample will include 20 prematurely born children who experienced hypoxic insults during postnatal life. To allow comparison to “normative” expectations, we will compare these 20 former preterm children with 10 healthy term-born controls without exposure to hypoxia and of similar age, sex, race distribution as the preterm group. Data from these 30 children will be used to develop appropriate sample sizes, using actual rather than predictive data, for future studies characterizing neural structure and function following postnatal hypoxic insults.

Specific structural and functional characteristics used in our analyses will include

- apparent diffusion coefficients and fractional anisotropy generated from DTI data
- fMRI-BOLD, measured during the pediatric verbal n-back, and HD-EEG sLORETA

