- neurobehavioral assessment results (grooved pegboard test, verbal n-back, Child Behavior Checklist, Vanderbilt Assessment test, Child’s Sleep Habits Questionnaire, Pediatric Sleep Questionnaire)

Covariates include 1) age, 2) sex, 3) race, 4) preterm vs. term birth, and 5) frequency of hypoxic insults (< 5000 versus ≥ 5000) during the first 8 weeks of life within the preterm group. The continuous outcome measure variables will be summarized using descriptive statistics (mean, standard deviation, median, interquartile range). Frequency analyses and stem-n-leaf graphs will characterize data distributions. Skewed continuous variables will be transformed to satisfy normality assumptions of hypothesis testing. Outcome measures for the two groups will be compared graphically using box plots. We will perform hypothesis tests for equality of data distribution for the two groups using t-tests or Wilcoxon sign rank test, as appropriate, with a significance level of 10%.

As we are interested in the differences of above mentioned outcome measures in two groups, we will focus on effect size estimation for the differences of our measures. To detect significant effect size, we will perform regression analysis on the outcomes of interest with the primary covariate of interest being group membership (preterm vs. term birth). In the regression analyses, we will control only for significant confounding effects of age, sex, race, and frequency of hypoxic insults. Using regression analyses, we will determine point

estimates, regression coefficients (beta), as well as 90% confidence interval of betas. The confidence intervals will be main estimated effect size or the differences in outcomes in two groups due to preterm and term birth.

Confidentiality of Specimens and Banking

I am not storing specimens in this research project – *please leave the rest of this section blank*

Describe:

- The source of the specimens*
- Where the specimens will be stored*
- How long the specimens will be stored*
- How the specimens will be labeled*
- How the specimens will be accessed*
- Who will have access to the specimens*
- When and how will the specimens be destroyed*
- How will the specimens be transported (Please note if transporting specimens, a Material Transfer Agreement (MTA) is required).*

Describe:

- The procedures to release specimens including:*
 - i. The process to request a release*
 - ii. Approvals required for a release*
 - iii. Who can obtain specimens*

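### Hypoxic-insult frequency, defined only among preterm children, is listed as a conditional confounder in the preterm-versus-term regression; when it is retained with controls in the <5000 class, the group coefficient is no longer the preterm-term difference

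*Combined protocol and SAP*

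**What the plan says.** All the analysis text is in the Data Analysis Plan section of the combined protocol and SAP. The fifth covariate is "frequency of hypoxic insults (< 5000 versus ≥ 5000) during the first 8 weeks of life within the preterm group". Preterm versus term birth is the primary covariate of interest in the regressions. The adjustment rule is: "In the regression analyses, we will control only for significant confounding effects of age, sex, race, and frequency of hypoxic insults". The plan then interprets the 90% intervals for the coefficients: "The confidence intervals will be main estimated effect size or the differences in outcomes in two groups due to preterm and term birth".

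The comparison group is "10 healthy term-born controls without exposure to hypoxia". The Study Design, Procedures and Timeline section gives the purpose of the comparison as "to determine whether differences in birth events and oxygen levels during the newborn period lead to structural and functional impairment". On use of the results, the plan says: "Data from these 30 children will be used to develop appropriate sample sizes".

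Recruitment Methods provides a fallback, "In the event that we cannot enroll 20 children who have continuous oxygen saturation data from their neonatal hospital stay", under which other preterm survivors may be recruited. The documents do not say what value term children, or preterm children without saturation records, take on the hypoxia covariate. They describe no preterm-only model.

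**The concern.** A confounder is a separate cause of the outcome that is unevenly distributed between the groups. Neonatal hypoxia is not that here. By the study's own design it is part of the exposure that distinguishes preterm from term children, and controls have none of it. Adjusting the group comparison for it changes the question that the group coefficient answers.

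Because the term is kept only when significant, the question could also change from one outcome to the next. For one DTI measure the coefficient might be all preterm minus term, and for the next fMRI or behavioural measure low-exposure preterm minus term. Both would be reported as the preterm-term difference. Estimating those differences is the main purpose of this pilot, and its data are meant to size later studies.

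**Working it through.** The plan states no power, effect size or SD, so there is no figure of its own to reproduce. The check is algebra followed by an illustrative simulation.

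**Inputs from the documents.** 20 preterm and 10 term children; a binary hypoxia class (<5000 or ≥5000); controls unexposed; 90% intervals.

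**Assumed, because the documents do not give them.** 5, 10 or 15 of the 20 preterm children at ≥5000; unit residual SD; the effect sizes shown; the retention threshold (p<0.10, with p<0.05 as a check).

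**Step 1: what the coefficient estimates.** Fit Y = a + b·preterm + c·H, with H = 1 for ≥5000 and 0 otherwise. Controls, with no insults, have H = 0. Least squares gives:

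- b = mean(preterm <5000) − mean(term)
- c = mean(preterm ≥5000) − mean(preterm <5000)
- overall preterm-term difference = b + p·c, where p is the share of preterm children at ≥5000

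So b misses the overall difference by p·c. With low-exposure preterm minus term = −0.3 SD and c = −0.6 SD:

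| Preterm children ≥5000 | p·c | Overall difference | b |
|---|---|---|---|
| 5 of 20 | 0.25 × −0.6 = −0.15 | −0.45 | −0.30 |
| 10 of 20 | 0.50 × −0.6 = −0.30 | −0.60 | −0.30 |
| 15 of 20 | 0.75 × −0.6 = −0.45 | −0.75 | −0.30 |

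**Step 2: precision.** Without the term, the SE of b is √(1/20 + 1/10) = 0.387 SD. With it, the SE is √(1/n_low + 1/10), where n_low is the number of preterm children below 5000. This is 0.408, 0.447 or 0.548 SD for n_low = 15, 10 or 5. The 90% half-width rises from 0.66 to 0.70, 0.76 or 0.93 SD.

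**Step 3: other codings.** If controls are set to missing, a complete-case fit drops all 10. The design matrix then has rank 2 for 3 columns, and b cannot be estimated. If H is centred within the preterm group and controls are set to 0, b equals the overall difference again (−0.45, −0.60, −0.75) with SE 0.387.

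**Step 4: the conditional rule.** This simulation used 40,000 replicates per scenario, no other covariates, controls coded <5000, and the term kept if p<0.10. Effects are for <5000/≥5000 preterm children against term, in SD units.

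| n_low | Effects | Truth | Term kept | Mean b | 90% CI coverage |
|---|---|---|---|---|---|
| 10 | −0.6/−0.6 | −0.60 | 10% | −0.60 | 88% |
| 10 | −0.5/−0.7 | −0.60 | 13% | −0.56 | 88% |
| 15 | −0.3/−0.9 | −0.45 | 31% | −0.36 | 88% |
| 10 | −0.3/−0.9 | −0.60 | 37% | −0.41 | 82% |
| 5 | −0.3/−0.9 | −0.75 | 31% | −0.49 | 79% |
| 10 | −0.9/−0.3 | −0.60 | 37% | −0.80 | 82% |

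In the fourth row, power is 31%, against 43% for the model with group alone. Keeping the term at p<0.05 instead gives a mean of −0.46 and 84% coverage. With the centred code, the same case gives −0.60 and 90%.

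These averages include the replicates in which the term was dropped. Among those that kept it, the fourth row has mean b −0.08 with coverage about 70%, and the fifth row has +0.12 (truth −0.75) with coverage about 52%. The retained models are the ones a reader would see reported as adjusted.

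**The case against.** The strongest reply is that the plan assigns controls no value on this covariate. It names two classes within the preterm group, which could point to a preterm-only analysis, and a coding of those same classes exists that leaves the group contrast intact. On this view the fault is missing detail. It is true that the coding is unstated. However, the regression sentence lists hypoxia frequency beside age, sex and race in the model whose main regressor is birth group, and no preterm-only model appears. Unexposed controls also fall naturally into the <5000 class. A team following the text would therefore obtain the altered contrast.

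Other parts of the reply stand:

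- The effect sizes are assumed, and the −0.3/−0.9 case is a strong one. With −0.5/−0.7 the average bias is only about 0.04 SD.
- In the 10/10 strong case the term is dropped in 63% of replicates. The average shift of about 0.19 SD is half the unadjusted SE of 0.387.
- The 10% level in the plan belongs to the two-group tests, so the retention threshold used here is a guess.
- A rank-deficient fit would be noticed and would not produce a misleading result.
- Sizing a trial on any point estimate from 30 children is unreliable, whichever model is used.
- The unadjusted tests and descriptive summaries are unaffected and could be used for sizing.
- With 42 children in the cohort, recruits without saturation records may never be needed.

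**Conclusion.** The concern holds and should be fixed before analysis. As written, the rule puts a component of the exposure into the group model as a confounder. When the term is retained with controls in the <5000 class, the coefficient labelled as the preterm-term difference is low-exposure preterm minus term. That result is algebraic and depends on no assumed effect.

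The size does depend on assumptions. The average bias is nil when hypoxia has no effect within the preterm group, small when the effect is modest, and substantial when it is large. It can go in either direction. Interval coverage in the simulated scenarios ran from 79% to 88% against a nominal 90%. The rule retains the term when the estimated within-preterm effect is large relative to its error, and for a given split that is when the shift is greatest. A retained term does give a coarse within-preterm hypoxia contrast, so the information is useful but is in the wrong model.

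**What to change.** Remove hypoxic-insult frequency from the covariates of the preterm-versus-term regressions, and report that group coefficient with its 90% interval as the preterm-term difference.

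Add a separate regression among preterm children with saturation records, with hypoxia as the regressor and age, sex and race handled under the same rule as in the group model. Base statements about hypoxia on this model. Entering the insult count as a continuous variable is preferable but secondary. Preterm children without saturation records stay in the group comparison only.

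If one joint model is preferred, state the coding: the ≥5000 indicator centred within the preterm group, with controls set to 0. The plan must then also say how preterm children without records are handled.

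The cost is a few sentences in the plan and one further small-sample model. No new data are needed, because saturation was recorded continuously in the primary cohort. The hypoxia model will be imprecise with at most 20 children and should be reported as such.

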Purpose: Our goal is to characterize structure and function of dopaminergic pathways and the cortical regions innervated by those pathways in post-hypoxic former preterm children. We hypothesize that dopaminergic projections, originating in the substantia nigra pars compacta (SNpc) and ventral tegmental area (VTA), projecting primarily to the striatum and prefrontal cortex (PFC) to modulate motor control and cognitive function, will be structurally and functionally impaired. Our primary study cohort is comprised of former preterm children born in 2004-2010 with birth gestational age between 22-28 weeks in whom we have characterized their postnatal hypoxic exposure continuously during their first eight weeks of life. To meet recruitment targets, we may additionally recruit additional former preterm children born between the ages of 9 and 17 years old at consent, with birth gestational age between 22-30 weeks and birth weight appropriate for gestational age (AGA). For comparison, we plan to also recruit healthy control children based on eligibility criteria (between the ages of 9 and 17 years at time of consent; without diagnosis of autism, epilepsy, metallic implants, dental braces, or those who have been treated for a concussion), and who are within the age range of the eligible former preterm children at the time of consent.

Specific Aim 1: We will quantify and compare the structural integrity of dopaminergic circuits originating in the substantia nigra pars compacta (SNpc) and ventral tegmental area (VTA) that project to striatum, prefrontal cortex, and nucleus accumbens, in post-hypoxic former preterm children versus healthy control children born at term within the age range of the eligible former preterm children.

Specific Aim 2: We will quantify and compare functional activity during tasks that engage executive function within cortical brain regions of post-hypoxic former preterm children versus healthy control children born at term within the age range of the eligible former preterm children at the time of consent. Our emphasis will be upon the prefrontal cortex which receives projections from the SNpc and VTA.

Hypothesis 1: Post-hypoxic former preterm children will manifest significantly reduced white matter density within dopaminergic circuits originating from the SNpc and VTA when compared to healthy controls.

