Hypothesis 2: Post-hypoxic former preterm children will exhibit reduced activity within cortical networks innervated by the SNpc and VTA when compared to healthy controls.

Background

1. *Describe the relevant prior experience and gaps in current knowledge describing how it will add to existing knowledge.*
2. *Describe any relevant preliminary data.*
Please add relevant references at the end of the protocol, not at the end of this section.

Hypoxic insults occurring during the perinatal period remain the leading cause of permanent brain impairment.¹ Apparent cognitive and motor dysfunction, such as that

seen in cerebral palsy, will occur in 4-10% of those post-hypoxic newborns.^{2,3} Subtle impairment, such as that seen in disorders of minimal brain dysfunction will occur in > 3 million post-hypoxic newborns.^{4,5} Collectively, hypoxia-induced morbidity and mortality afflicts 3% of all newborns, worldwide, and leads to substantial personal and socioeconomic burden.⁶

Specific neuropathology, elicited by subtle hypoxic insults that lead to cognitive dysfunction, is not well described in humans. Over 84% of preterm infants experience apnea of prematurity with accompanying intermittent hypoxia.^{7,8} Neuropathology, cognitive impairments, and motor impairments induced by *severe* hypoxic insults are well described⁹ and frequently lead to a clinical diagnosis of cerebral palsy.^{6,10} Cognitive and motor deficits are also associated with *mild to moderate* hypoxic insults,¹¹ but the specific neuropathology is poorly defined. Mild to moderate hypoxic insults resulting from apnea of prematurity do not elicit the overt neuropathology observed following severe hypoxic events. As such, standard neuroimaging and diagnostic techniques,¹² with the exception of positron emission tomography requiring infusion of radioactive ligands,¹³ have failed to identify major changes in brain structure or function. Nonetheless, disorders of minimal brain dysfunction and cognitive impairments do exist.¹⁴⁻¹⁶

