diffusion tensor imaging with subtraction analyses and fMRI coupled with high-density electroencephalographic (EEG). We hypothesize that dopaminergic projections, originating in the substantia nigra pars compacta (SNpc) and ventral tegmental area (VTA), projecting primarily to the striatum and prefrontal cortex (PFC) to modulate motor control and cognitive function, will be structurally and functionally impaired. The primary sample for our proposed study is derived from a cohort of preterm infants admitted to Rainbow Babies & Children’s Hospital between 2004 and 2009 at a gestational age of 23 to 28 weeks. The purpose for developing the original cohort was to establish the effects of maintaining oxygen saturation levels between 85%-95% to decrease the development of retinopathy of prematurity. Oxygen saturation levels and desaturation events were recorded continuously from the first day of life to 8 weeks’ postnatal age. If recruitment targets for study group children cannot be achieved, we will engage the assistance of Co-Investigator [name] to recruit additional former preterm children currently 9 to 17 years old with birth gestational age between 23-30 weeks and birth weight appropriate for gestational age (AGA for comparison, we plan to recruit healthy control children within the age range of the eligible former preterm children. Our findings will provide new insight into the neural basis of cognitive dysfunction reported in many former preterm children who experienced mild to moderate hypoxic insults.

APPROACH: Eligible and interested former preterm children will be identified by [name] and [name]. These children are prematurely born survivors from Rainbow Babies & Children's Neonatal Intensive Care Unit, and have been followed since birth. Children in this cohort have already participated in research, and remain willing to participate in future projects. [name] and/or [name] will provide our research team with names/contact information of interested individuals. We will contact those individuals by telephone to describe the study and conduct a prescreening.

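### The only hypoxia variable is an event count cut at 5000, although saturation levels were recorded continuously and could support a continuous rate and one burden measure

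*Combined protocol and SAP*

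**What the plan says.** The Data Analysis Plan lists five covariates. The fifth is "frequency of hypoxic insults (< 5000 versus ≥ 5000) during the first 8 weeks of life within the preterm group", and it is the only measure of hypoxia in the plan. It enters the regressions conditionally: "we will control only for significant confounding effects of age, sex, race, and frequency of hypoxic insults". The covariate of main interest in those regressions is group membership, preterm versus term.

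The section on study design, procedures and timeline states the question in terms of newborn oxygen levels, and describes the source data for the primary cohort: "Oxygen saturation levels and desaturation events were recorded continuously from the first day of life to 8 weeks". The Purpose section says of the same children that "we have characterized their postnatal hypoxic exposure continuously during their first eight weeks of life". The inclusion section likewise describes that cohort as having saturation level data over the first 8 weeks.

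Severity matters to the rationale. The Background says that "Mild to moderate hypoxic insults resulting from apnea of prematurity do not elicit the overt neuropathology observed following severe hypoxic events", and the design section expects the findings to bear on "cognitive dysfunction reported in many former preterm children who experienced mild to moderate hypoxic insults".

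The documents do not define a hypoxic insult by saturation limit or minimum duration, and they give no reason for the 5000 cut. They do not mention event depth, time below a limit, a rate per recorded hour, or usable recording time. The only saturation figures are in the account of why the source cohort was formed, which was to study "maintaining oxygen saturation levels between 85%-95% to decrease the development of retinopathy of prematurity". That is a target range, not an event definition. Recruitment Methods allows preterm children from outside the recorded cohort if 20 with recordings cannot be enrolled.

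**The concern.** The stated question is about oxygen levels, and the recordings hold oxygen levels. The analysis variable keeps only which side of 5000 a child's event count falls on. Two kinds of information are lost: differences in frequency within each category, and anything about how deep the events were or how much time they took up in total.

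At stake is what the pilot can say about hypoxia among the preterm children. The Data Analysis Plan says the data will be used to size later studies of brain structure and function after postnatal hypoxia, so a coarse exposure measure would carry into that planning. The preterm-versus-term difference does not depend on how hypoxia is measured within the preterm group, except where the fifth covariate is kept as an adjustment.

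**Working it through.** The plan gives no derivation of the 5000 cut, so there is no figure to reproduce. The check asks what the cut means over the stated window and how much exposure can differ at the same coded value.

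**Inputs from the documents:** cut = 5000 events; window = 8 weeks = 56 days = 56 × 24 = 1344 h; at most 20 preterm children with recordings.

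**Assumed inputs:** mean event duration, the example counts other than 5000, and the share of the window with usable recording.

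**Step 1: the cut as a rate.** 5000 / 56 = 89.3 events per day; 5000 / 1344 = 3.7 per hour.

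**Step 2: information lost by the cut.** Children with 5000 and 6000 events differ by 1000 / 56 = 17.9 events per day and share a category. Children with 4900 and 5000 events differ by 100 / 56 = 1.8 per day and are placed in different ones.

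**Step 3: cumulative time at the same count.** Hours in desaturation = 5000 × mean seconds / 3600; percent of window = hours / 1344.

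| Mean duration (assumed) | Hours | Percent of 8 weeks |
|---|---|---|
| 5 s | 6.9 | 0.5 |
| 10 s | 13.9 | 1.0 |
| 40 s | 55.6 | 4.1 |
| 60 s | 83.3 | 6.2 |

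The 10 s and 40 s rows differ fourfold with an identical count. The whole range is 60 / 5 = 12-fold.

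**Step 4: the order can reverse.** 4000 events of 60 s give 4000 × 60 / 3600 = 66.7 h and are coded low. 6000 events of 10 s give 6000 × 10 / 3600 = 16.7 h and are coded high.

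**Step 5: usable recording time, if it varied.** The true 8-week total needed to reach 5000 recorded events is 5000 / coverage: 5000 at 100%, 5556 at 90%, 6250 at 80% and 10,000 at 50%. A child with 6200 true events and 80% coverage would show 0.8 × 6200 = 4960 and be coded low. The documents do not say that coverage was incomplete, so this step only shows why valid hours should be reported.

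**The case against.** The best defence is that event frequency suits the construct. The Background and the section on potential benefit describe intermittent hypoxia, for which counting episodes is reasonable. The documents do not establish that cumulative burden is the quantity that does harm. This stands: it argues for keeping frequency as the leading measure, and against replacing it with burden. It does not justify cutting the count in two.

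Several stronger readings are tempting, but the documents do not support them.

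- A reader might infer that the count is wholly blind to depth and duration. Recording desaturation events requires some criterion, and the cohort's definition may include a threshold or minimum duration. The documents do not give it.
- A reader might infer that recording time differed between children. The documents describe continuous recording over one fixed window and report no gaps. What is missing is a plan to check usable hours.
- A reader might infer that any hypoxia effect is pulled toward zero. That needs burden to be the true exposure and the misclassification to be unrelated to outcome. Neither is shown.
- A reader might infer that the main result is compromised, or that a within-preterm dose-response analysis is invalid. The main contrast is preterm versus term in an exploratory pilot, hypoxia frequency is a conditional covariate, and no separate within-preterm model is specified.
- A reader might infer that the study cannot tell mild from severe exposure and that a burden measure would cure this. Selection already removes some severely affected children, for example through the exclusion of preterm children with a developmental index below 80 at two years. Time below one limit also supplies no boundaries between mild, moderate and severe.

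The objection that adding several correlated exposures in at most 20 children brings its own problems also stands, and it limits the fix to one added measure.

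**Conclusion.** The point holds in a limited form. The plan reduces continuous saturation recordings to a two-level event count. That discards variation within each category and makes no use of depth or cumulative time, although the study asks about oxygen levels. Children in the same category can differ fourfold in time in desaturation if mean event duration runs from 10 s to 40 s, and 12-fold from 5 s to 60 s. These durations are assumptions, so the ratios illustrate what is possible and do not estimate what happened in this cohort.

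The consequence is confined to statements about hypoxia among preterm children. The main preterm-versus-term comparison is not undermined, and the direction of any bias is unknown. The improvement is worthwhile because it draws on recordings that the documents describe as available.

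**What to change.** In the Data Analysis Plan, under the fifth covariate:

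1. For preterm children with recordings, replace the two-level variable with a continuous rate, events per valid recorded hour. Use the source cohort's event definition and state it in the plan.
2. Add one burden measure from the same recordings as a secondary exposure: percent of valid recording time below a single saturation limit, fixed before analysis.
3. Keep the 5000 cut as a sensitivity analysis.
4. Report valid recorded hours for each child.
5. Leave preterm children without recordings out of these exposure analyses, and say so. They can stay in the preterm-versus-term comparison.

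The cost is a paragraph of text and some reprocessing of at most 20 recordings, with no change to visits, burden on families or sample size. There are two drawbacks. The burden measure is one more, probably correlated, exposure in a small exploratory sample, so it should be labelled secondary. It also depends on the stored recordings having enough resolution, which the documents do not describe and which should be checked before the measure is written into the plan.
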